4.0 Test Schedule

Tests and procedures	Active Monitoring				
	Baseline				Until PD or patient refusal
	≤21 days prior to registration	Cycle 1 Pre-RT Scans	Cycle 1 RT	Cycle 2 Post RT Scans ⁵ ≤42 days after RT	At every clinically indicated follow-up MR scan (end of each new cycle)
Physical exam, wt, ECOG PS	X				
Neuro history and exam	X			X	X
MMSE ⁴		X ¹²		X	X
CT simulation for radiotherapy planning	X ^{8,9}				
Pregnancy test		X ^{1,R}		X ^{1,R}	X ^{1,R}
¹⁸ F-DOPA-PET ^R		X ⁸		X	X ³
MRI with contrast/ RANO Assessment		X ^{6,8}		X	X ³
Advanced MRI		X ^{7,8}		X	X ³
¹⁸ F-DOPA adverse event assessment		X ²		X ²	X ²
Adverse event assessment ¹¹ (See Section 10.3)	X		X ¹⁰	X	X
QOL assessment ⁴		X ¹²		X	X
Concurrent Steroids and Anticonvulsants		X ¹²		X	X
MGMT Methylation Status	X ¹³				

1. For women of childbearing potential only. Must be done ≤48 hours prior to injection of study drug. Note: For a positive pregnancy test prior to the pre-RT ¹⁸F-DOPA injection the patient will not undergo the ¹⁸F-DOPA PET scan and will instead be taken off study with no follow-up. For any post-RT ¹⁸F-DOPA injection, the patient will not undergo the ¹⁸F-DOPA PET scan and will instead move to event monitoring.
2. ¹⁸F-DOPA post-injection assessment: done approximately 15-20 minutes post injection of ¹⁸F-DOPA and if AE observed a second AE assessment is required ≤24 hours post injection.
3. All follow-up serial imaging after initial treatment until progression up to 5 years. Note a typical grade IV follow-up schedule will include follow-up scans every 2 months for the first year after

radiation therapy, every 3 months for the second year, every 4 months for the third year, every 6 months after that. The actual timing of the follow-up scans for an individual patient will be per the clinician's discretion, e.g. if the clinician suspects possible progression, they may schedule more frequent follow-up imaging. While it is extremely unlikely (as current time to progression is 6 to 9 months), if a grade IV patient did not progress for 5 years, they may have up to 16 follow-up visits.

4. Patient will complete a maximum of 6 post-baseline QOL/MMSE evaluations
 5. Post RT scans to occur 3 to 6 weeks after RT is complete, to coordinate with first follow-up appointment
 6. Pre-treatment measurement

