13.0 Follow-up Decision at Evaluation of Patient

- 13.1 A patient is deemed *ineligible* if after registration, it is determined that at the time of registration, the patient did not satisfy each and every eligibility criteria for study entry. The patient will go off study.
- If the patient received MR and PET for radiotherapy planning, all data up until the point of confirmation of ineligibility must be submitted.
 - If the patient never received pre-RT PET, on-study material must be submitted.
- 13.2 On-study material and the End of Active Treatment/Cancel Notification Form must be submitted for patients who *cancel* participation prior to the start of pre-RT PET. These

materials must be provided to the MCCC Operations office. All data up to the point of going off study must be submitted to the MCCC Operations Office. No additional follow-up will be necessary.

- 13.3 Those patients who will *not* receive ^{18}F -DOPA PET image-guided dose escalation radiation treatment *or* who will receive radiation treatment elsewhere (other than specifically listed in section 6.4) will move to Event Monitoring phase.
- 13.4 Patients remain on study and continue to receive ^{18}F -DOPA PET scans at each clinically indicated MR scan until all of the following are confirmed / complete (up to 5 years or patient refusal):
- Radiological progression by central review per RANO criteria
 - Clinical progression identified by the treating oncologist
 - Because of the difficulty determining pseudoprogression from progression, and bevacizumab can be used to treat either progression or radiation-related treatment changes, treatment with bevacizumab alone does not qualify as progression. Clinical progression is determined by treating oncologist or initiation of systemic salvage regimens other than bevacizumab.
 - It is more than 3 months since radiation treatments have been completed, to ensure the radiological evidence is tumor progression versus treatment response
 - Note: the ^{18}F -DOPA PET scan (study imaging) during the patient visit at the time the above three conditions are met is highly desired and the patient is to be encouraged to complete it even if it is scheduled after the patient has been informed they have progressive disease.
- 13.5 Patients who develop Confirmed PD (both clinical and radiologic progression) or withdraw from further ^{18}F -DOPA PET scans will go to the event-monitoring phase per Section 18.0.

14.0 Body Fluid Biospecimens - None.

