[76]. Time to disease progression is defined as the time from initial surgery to the earliest date documenting confirmed-progression. If a patient dies without documentation of disease progression, the patient will be considered to have had tumor progression at the time of death. If a patient is declared to be a major treatment violation, the patient will be censored on the date the treatment violation was declared to have occurred. In the case of a patient starting treatment and then never returning for any evaluation, the patient will be censored for progression on the last day of therapy. This analysis will be conducted split by MGMT-methylation status of the patients and historical control.

16.323 Overall Survival

Compare patient outcomes including overall survival after radiation therapy targeting volumes designed with both ^{18}F -DOPA PET and conventional MR image information with historical controls from Mayo Clinic Rochester patients. As described above for confirmed-progression free survival, we will analyze both historical control patients and our prospective dose escalation patients for overall survival. Survival time is defined as the time from initial surgery to death due to any cause. The distributions of survival times and comparisons between these two groups will be estimated using the method of Kaplan-Meier [76].

16.324 Quality of Life

Evaluate quality of life after radiotherapy treatment targeting dose escalated volumes defined to include high ^{18}F -DOPA PET uptake. Quality of life (QOL) will be compared to high-grade glioma patients treated on previous North Central Cancer Treatment Group protocols. QOL and cognitive function will be evaluated with the MD Anderson Symptom Inventory Brain Tumor Module (MDASI-BT) and Mini-Mental Status Exam (MMSE) questionnaires at baseline and at each MRI evaluation up to 6 evaluations to capture the quality of life profile and correlate findings with radiologic and clinical progression as well as time points used on prior studies to allow historical comparisons. The main QOL analysis will be the change from baseline to first subsequent MRI timepoint in the overall score from the MDASI-BT. All other QOL analysis will be exploratory and may include change percent from baseline to all timepoints using t-tests and generalized linear models to test for changes at each time point and non-zero slope respectfully.

16.325 Adverse Events

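### The exploratory longitudinal QOL analyses in 16.324 name no within-patient correlation and no handling of scores that stop at progression, so the slope may lose power and understate worsening

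*Combined protocol and SAP*

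**What the plan says.** Section 16.324 sets one main QOL comparison: "The main QOL analysis will be the change from baseline to first subsequent MRI timepoint in the overall score from the MDASI-BT". Note 5 of Section 4.0 times that visit: "Post RT scans to occur 3 to 6 weeks after RT is complete, to coordinate with first follow-up appointment".

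Everything else is secondary to it: "All other QOL analysis will be exploratory and may include change percent from baseline to all timepoints", and the sentence continues "using t-tests and generalized linear models to test for changes at each time point and non-zero slope respectfully". No random effect, GEE, other within-patient correlation or missing-data method is named for QOL.

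QOL and MMSE are collected in active monitoring, whose last column in Section 4.0 is headed "Until PD or patient refusal". Note 4 caps the evaluations at six after baseline. Section 13.5 covers the exit: "Patients who develop Confirmed PD (both clinical and radiologic progression) or withdraw from further" study PET scans "will go to the event-monitoring phase per Section 18.0". The event-monitoring forms in 18.13 include no QOL booklet or MMSE. Confirmed PD needs radiologic and clinical progression more than 3 months after RT (11.416, 13.4).

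**The concern.** Goal 2.23 asks how QOL fares after dose-escalated RT. The main comparison is early and cannot show later decline. The per-visit tests and the slope are the only named analyses that reach later QOL and cognition.

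Those later visits hold a shrinking group. Note 3 of Section 4.0 describes progression as early ("as current time to progression is 6 to 9 months"). Exit through confirmed PD includes clinical progression, which plausibly goes with a higher symptom burden. A model with independent rows, which the text would permit, ignores both the repeated scores and the reason they stop. On the MDASI-BT a higher score is worse, so losing worsening patients pulls the slope towards stability. The error therefore leans towards reassurance.

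**Working it through.** **Inputs from the documents.** Up to 6 post-baseline scores (4.0 note 4); scans about every 2 months in year 1 (4.0 note 3); historical CPFS6 of 59.3% (16.21); 72 grade IV patients (16.33, stated for the correlative endpoints). No QOL sample size, SD, effect size or completion rate is given, so there is no QOL figure to reproduce.

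**Retention.** Suppose exits follow an exponential curve through CPFS6. The hazard is −ln(0.593)/6 = 0.087 per month, and retention at t months is exp(−0.087t). At assumed visits 3.5, 5.5, 7.5, 9.5, 11.5 and 13.5 months from craniotomy this gives 74, 62, 52, 44, 37 and 31%, or 53, 45, 37, 31, 26 and 22 of 72. Early retention should be better than this, since confirmed PD cannot be declared until more than 3 months after RT.

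**Mechanism on change scores.** Write the score as Y(i,t) = a(i) + b(i)t + e(i,t). Change from baseline is b(i)t + e(i,t) − e(i,0).
- The patient level a(i) cancels. If all patients share one slope, exit related to the score need not bias the slope of change.
- The term e(i,0) is in every row from that patient. With a common slope, two rows have covariance σ² and variance 2σ², hence correlation 0.5. Independent rows ignore this, so the within-patient trend is estimated inefficiently.
- If b(i) varies and patients with steeper worsening leave sooner, the mean b(i) of those remaining falls with time, and the fitted slope is too small.

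**Simulation A** (n = 72; time per visit; between- and within-patient SD 1; true worsening 0.15 per visit; no exits before visit 2; exit related to observed scores).
- Common slope: the change-score model with independent rows is unbiased, with power 0.79 to 0.87 against 0.995 or more for the mixed model.
- Patient slopes with SD 0.15 to 0.25 per visit: the change-score slope falls to between 0.121 and 0.035. The shortfall is (0.15 − 0.121)/0.15 = 19% to (0.15 − 0.035)/0.15 = 77%. With no true average change, false rejection is 0.09 to 0.40. The mixed model gives about 0.15 and 0.04 to 0.05.

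**Simulation B** (n = 72; time per month; 0–10 score; baseline SD 1.2, residual SD 0.8, slope SD 0.08 per month; true worsening 0.10 per month; exits averaging the curve above; log hazard ratio 0.5 or 1.0 per 1.5 points of last score or per SD of own slope; 150 runs, so Monte Carlo error on rejection rates is up to about 8 points).

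| Exit depends on | Slope, change score, independent rows | Slope, mixed model | False rejection, independent rows | False rejection, mixed model |
|---|---|---|---|---|
| nothing | 0.100 | 0.099 | 0.07 | 0.05 |
| last score, 0.5 | 0.086 | 0.100 | 0.09 | 0.05 |
| last score, 1.0 | 0.080 | 0.101 | 0.17 | 0.03 |
| own slope, 0.5 | 0.056 | 0.076 | 0.43 | 0.29 |
| own slope, 1.0 | 0.046 | 0.067 | 0.68 | 0.61 |

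The change-score shortfall is 14% and 20% when exit follows the observed score, and 44% and 54% when it follows the patient's own slope. In the latter case the mixed model also falls short, by 24% and 33%. With exit unrelated to QOL there is no bias, and power is 0.95 against 0.99.

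Both simulations used absolute change. The plan says percent change, which was not simulated.

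**The case against.** The case against is substantial.

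- **Status.** The slope is exploratory and optional, and no QOL result enters a decision rule. Toxicity has its own endpoint (16.325) and suspension rule (16.42). This stands and limits the weight of the point.
- **Main analysis.** A reader might infer that the QOL endpoint as a whole is compromised. It is not. The main comparison falls 3 to 6 weeks after RT, before confirmed PD can be declared; only death or refusal can thin it.
- **Departure instead of change.** A reader might infer that the slope shows only who left, or that it could report improvement while every patient worsens. The planned outcome is change from baseline, so the slope carries both. In every run with true average worsening the mean fitted slope stayed positive.
- **Raw-score figures.** Independent rows on raw scores do much worse: with a common slope, false rejection of 0.11 to 0.60. Those figures do not carry over, because subtracting baseline removes the patient level.
- **The t-tests.** A per-visit test of change compares remaining patients with their own baseline, so it does not set everyone's early visits against late survivors. It does describe only those still observed.
- **Silence on correlation.** The text does not state that rows are independent; that is an inference. It stands as a caveat, but an analyst could fit independent rows and comply.
- **Preliminary progression** does not end collection, so some scores during deterioration are captured.
- **Favourable comparison.** The mixed model used the baseline row as an outcome and matched the way the data were generated, so its advantage is somewhat flattering.

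**Conclusion.** The point holds for the exploratory longitudinal QOL and MMSE analyses only. As written, they permit a model that ignores repeated scores and exit at progression. On change scores that model loses power even without bias. It understates worsening when patients' slopes differ and exit is related to QOL: by 14% to 77% across the settings above, with false rejection of about 0.09 to 0.68 when there is no true average change. If exit is unrelated to QOL, or all patients share one slope, there is no bias.

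The size rests on assumed SDs, slope variation, visit times, exit pattern and exit–QOL association, none of them in the documents. Only the direction and range should be used. Neither the primary endpoint nor the main QOL comparison is threatened.

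**What to change.** In 16.324, for the longitudinal MDASI-BT and MMSE analyses, replace the generalized linear model and visit-by-visit t-tests with a likelihood-based linear mixed model:

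- outcome: the scores themselves, with baseline and all later visits as outcomes;
- time as a fixed effect, with a patient random intercept and, where estimable, a random slope;
- the slope and the visit contrasts against baseline both taken from this model;
- numbers contributing and reasons for missing scores reported at each visit;
- a pattern-mixture display of mean profiles by last QOL visit.

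Leave the main baseline-to-first-MRI comparison as it is.

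The cost is SAP wording and a little more analysis work, with no new patients, visits or forms. The mixed model removes the bias when exit depends on observed scores but only reduces it when exit depends on unobserved worsening. The display is therefore part of the fix, and conclusions should be worded accordingly.

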10.6 Required Routine Reporting

Adverse events related to PET scanning and PET tracer injection to be graded if detected during observation post injection, or if noted within 24-hour post PET tracer injection per the CTCAE v4.0 grading. Adverse events related to dose escalation will be graded at baseline, assessed during RT and reported at the end of RT, and during every clinically indicated MR follow-up during Active Monitoring until progression.

Category (CTCAE SOC)	Adverse event/Symptoms	Baseline	Post injection assessment ¹	Active Monitoring
General disorders and administration site conditions	Fatigue	X		X
Immune system disorders	Allergic reaction		X	
Nervous system disorders	Central nervous system necrosis			X
Nervous system disorders	Vasovagal reaction		X	
Injury, poisoning and procedural complications	Bruising	X	X	
Skin and subcutaneous tissue disorders	Rash maculo-papular	X	X	

1. This assessment should occur approximately 15-20 minutes post injection (after scan is completed).

10.61 Additional instructions:

Submit via appropriate MCCC Case Report Forms (i.e., paper or electronic, as applicable) the following AEs experienced by a patient and not specified in Section 10.6:

- 10.611 Grade 2 AEs deemed *possibly, probably, or definitely* related to the study treatment or procedure.
- 10.612 Grade 3 and 4 AEs regardless of attribution to the study treatment or procedure.
- 10.613 Grade 5 AEs (Deaths) (See [Section 10.52](#))

10.62 Late Occurring Adverse Events:

Refer to the instructions below and in the Forms Packet (or electronic data entry screens, as applicable) regarding the submission of late occurring AEs following completion of the Active Monitoring Phase (i.e., compliance with Test Schedule – see [Section 4.0](#)).

Toxicity will be monitored continuously as each patient is accrued and follow-up data are accumulated. Acute radiation therapy and chemotherapy toxicities will be graded using Common Terminology Criteria for Adverse Events (CTCAE) v4.0 (available at <http://ctep.cancer.gov>). Late toxicities will be reported using the RTOG/EORTC late toxicity criteria [71].

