16.22 Sample Size

The two-stage design to be utilized is fully described in Section 16.21. A minimum of 25 and a maximum of 45 Grade-IV MGMT un-methylated evaluable patients will be accrued to this phase-II study unless undue toxicity is encountered. We anticipate accruing an additional 5 Grade-IV MGMT un-methylated patients to account for ineligibility, cancellation, major treatment violation, or other reasons. We also anticipate accruing a total of 25 Grade-IV MGMT methylated, 12 Grade-IV patients with unknown MGMT status, and 6 grade-III patients. Maximum projected accrual is therefore 87 grade-IV patients and 6 grade-III patients. We anticipate pre-registering 150 patients to register these 93 patients necessary for the study design.

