Determine acute and late effect toxicity after radiotherapy treatment targeting dose escalated volumes defined to include high ^{18}F -DOPA PET uptake. The rate of acute and late treatment-related toxicities for newly diagnosed high-grade glioma patients treated with ^{18}F -DOPA PET image-guided dose escalation will be determined, with acute RT toxicities graded using Common Terminology Criteria for Adverse Events (CTCAE) v4.0 (available at <http://ctep.cancer.gov>), and late toxicities reported using the RTOG/EORTC late toxicity criteria [71]. Patients will be considered evaluable for adverse events if they receive ^{18}F -DOPA PET or ^{18}F -DOPA PET image-guided dose escalation RT.

16.326 Compare confirmed-progression free survival at 12 months for Grade IV MGMT-methylated patients after radiation therapy targeting volumes designed with both ^{18}F -DOPA PET and conventional MR image information with historical controls from Mayo Clinic Rochester patients, including those on clinical trials.

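### Section 16.325 gives one evaluability rule for all adverse events; applied to radiotherapy toxicity, it adds patients who were scanned but never boosted and biases the rate low

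*Combined protocol and SAP*

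**What the plan says.** Section 16.325 (Adverse Events) carries out secondary goal 2.24. Its aim is "Determine acute and late effect toxicity after radiotherapy treatment targeting dose escalated volumes" that include high PET uptake. It then names the quantity to be reported: "The rate of acute and late treatment-related toxicities for newly diagnosed high-grade glioma patients treated with" PET image-guided dose escalation. It closes with the evaluability rule: "Patients will be considered evaluable for adverse events if they receive" 18F-DOPA PET or PET image-guided dose-escalation RT. No sentence gives RT toxicity a denominator of its own.

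Section 10.6 keeps two streams of events apart. For the tracer: "Adverse events related to PET scanning and PET tracer injection to be graded if detected during observation post injection" or within a day of it. For the boost: "Adverse events related to dose escalation will be graded at baseline, assessed during RT and reported at the end of RT", and again at follow-up scans during active monitoring. Section 10.3 likewise has separate attribution scales for the two.

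Section 13.3 provides for patients who will not get the dose-escalated treatment, or "who will receive radiation treatment elsewhere (other than specifically listed in section 6.4) will move to Event Monitoring phase". Section 13.1 provides for patients found ineligible after MR and PET for planning.

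Section 16.22 states the allowance for the primary cohort: "We anticipate accruing an additional 5 Grade-IV MGMT un-methylated patients to account for ineligibility, cancellation, major treatment violation, or other reasons".

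**The concern.** The rate sentence in 16.325 points to one population, and the evaluability rule that follows defines a larger one. An analyst who applies the explicit rule to the one analysis the section describes would divide RT toxicities by everyone scanned.

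Patients scanned but not boosted would then enter as event-free. They receive no trial boost. Those who leave under 13.3 also go to event monitoring, and the form schedule for that phase (18.13) lists only the Event Monitoring Form and imaging at progression, with no RT adverse event form. They can add to the denominator but not to the numerator.

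At stake is the safety estimate for the 76 Gy boost, which is the experimental part of the treatment. The error can go only one way, towards a safer-looking regimen.

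**Working it through.** **1. Accrual figures (16.22).** Un-methylated: 45 evaluable + 5 extra = 50. All grade IV: 50 + 25 methylated + 12 of unknown status = 87. With 6 grade III: 93. These agree with the plan's totals. The plan states no toxicity rate and no adverse event denominator, so there is no figure of that kind to reproduce.

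**2. Who is in the evaluable set.** Sections 4.0 and 7.21 place the planning PET no more than 14 days before RT starts. Anyone who reaches the boost by the protocol pathway has therefore already qualified through PET. In practice the set is the boosted patients plus the PET-only patients.

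**3. Formula.** Let T be the number who began dose-escalated RT, P the number of PET-only patients, and x the number with an RT toxicity.

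- Rate in treated patients: x / T
- Rate in the 16.325 set: x / (T + P) = (x / T) × (1 − f), with f = P / (T + P)

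**4. Range for f (assumption).** The documents do not give P. The only stated allowance is 5 of 50 un-methylated patients, so f is taken from 0 to 5/50 = 10%. The upper end needs all 5 to have been scanned and none boosted.

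**5. Results.**

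| True rate | f = 0 | f = 5% | f = 10% |
|---|---|---|---|
| 10% | 10.0% | 9.5% | 9.0% |
| 20% | 20.0% | 19.0% | 18.0% |

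In counts, at the upper end: 9/45 = 20.0% becomes 9/50 = 18.0%, and 5/45 = 11.1% becomes 5/50 = 10.0%. If instead 5 of all 93 patients were PET-only, 9/88 = 10.2% becomes 9/93 = 9.7%.

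**6. Against sampling error at n = 45.** The normal-approximation 95% half-width is 1.96 × √(0.20 × 0.80 / 45) = 11.7 points at a 20% rate, and 1.96 × √(0.10 × 0.90 / 45) = 8.8 points at 10%. The largest shifts in the table are 2 points and 1 point.

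**7. The RT-toxicity rule in 16.42.** This rule uses a third base, patients enrolled, and acts above 10%. With 50 enrolled and 45 treated, more than 10% of enrolled means at least 6 patients (6/45 = 13.3% of treated). More than 10% of treated would mean at least 5 (5/45 = 11.1%). The choice of base can therefore change the count by one patient.

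**The case against.** The strongest reply is that 16.325 already restricts the rate. The sentence before the evaluability rule confines it to patients treated with dose escalation, and the rule itself speaks of adverse events in general. That stands. A reader might infer that the plan has fixed the wrong denominator, but no sentence says RT toxicity is divided by everyone scanned. The text supports a conflict between two adjacent sentences, not an established error.

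The wider set also has a proper use. Patients who had only the scan are at risk of tracer events and belong in that denominator. This too stands, and it is why the remedy is two sets rather than a narrower single one.

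Three stronger readings do not hold:

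- A reader might set the endpoint-evaluable patients, 45 + 22 + 5 + 4 = 76, against 93 and read a true 20% as 0.20 × 76/93 = 16.3%. The 22, 5 and 4 are counts as of 2/16/2017 (16.33, 16.321), while 93 is maximum projected accrual. Much of the gap may be patients not yet enrolled or not yet evaluable.
- A reader might count all cancellations as dilution. Those described in 13.2 occur before the pre-RT PET and so fall outside the set. Some ineligible patients were never scanned (13.1), and a patient with a major treatment violation may have begun RT. The 10% is therefore the ceiling of the allowance, not an expected value.
- A reader might infer a biased comparison with the historical controls. Section 16.1 notes that their toxicities were recorded, but 2.24 and 16.325 only set out to determine toxicity and plan no such comparison.

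It is also true that the effect is small and that the efficacy decision does not use this denominator.

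**Conclusion.** The point holds as an internal conflict in a prespecified safety analysis. If the evaluability rule is applied to RT toxicity, the reported rate is the true rate times (1 − f). On the stated allowance, that is a relative loss of 0 to 10%: at most 2 points at a true 20% and 1 point at a true 10%. If no patient is PET-only, or if the analyst follows the rate sentence instead, nothing changes.

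The size rests on two assumptions: that the un-methylated allowance bounds f (16.22 states no similar allowance for the other groups), and that PET-only patients contribute no RT toxicity. The direction does not depend on the value of f. The shift is well inside sampling error, but it is systematic, and it can be removed at almost no cost before the data are analysed.

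**What to change.** In 16.325, replace the single evaluability sentence with two sets:

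- patients injected with 18F-DOPA, for tracer and PET events;
- patients who began PET-guided dose-escalated RT, for acute and late RT toxicity.

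Report how many patients are in the first set but not the second, so that f can be seen. This matches the split already made in 10.3 and 10.6, and the treated-only evaluability of the primary endpoint in 16.21.

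The sponsor should also reconcile these sets with the RT-toxicity rule in 16.42 and state why the bases differ if they are meant to differ.

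The cost is about one sentence in the plan, with no new data to collect. The reported toxicity rate may come out slightly less favourable.
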